14.3. Analysis Populations

Safety Population:

All subjects who were administered any test article excluding subjects who drop out prior to administering any test article. At least one observation should be recorded.

Per-Protocol Population:

All subjects who have successfully completed all visits and did not substantially deviate from the protocol as determined by the trial cohort review committee prior to database hard lock (Per-Protocol Population). Justification of excluding subjects with protocol deviations in the per-protocol population set will be documented in a memo to file.

Intent-to-Treat (ITT) Population:

All randomized subjects regardless of actual treatment and subsequent withdrawal from study or deviation from protocol. At least one observation should be recorded.

14.4. Level of Statistical Significance

Co-primary endpoints will be tested using a 2-sided error rate of 5% each. Both primary hypotheses must be met in order to test the secondary hypothesis. A Bonferroni correction will be utilized for the adjustment of multiple secondary hypotheses using a 2-sided type I familywise error rate of 5%. All primary and secondary hypotheses must be met in order to test any exploratory hypotheses.

Exploratory hypotheses if tested, will utilize all available historical data in addition to data collected from the current study. Exploratory hypotheses will be tested sequentially by group, where all hypotheses in a preceding group must be met in order to continue any exploratory hypothesis testing. Within each grouping, a Bonferroni adjustment will be utilized to adjust for multiple testing.

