2.3. Hypotheses

All primary and secondary hypotheses must be met in order to satisfy the objective of this study.

Co-Primary Hypotheses

- 1. After approximately 1-week of wear in the optimized lenses, the Test lens will be superior to DT1MF with respect to clarity of vision in dim or low lighting conditions.
- 2. After approximately 1-week of wear in the optimized lenses, the Test lens will be superior to DT1MF with respect to clarity of vision when reading in dim light.

Both co-primary hypotheses must be met prior to testing the secondary hypotheses.

Secondary Hypotheses

- 1. After approximately 1-week of wear, the Test lens will be non-inferior to DT1MF with respect to clarity of distance vision. A non-inferiority margin of 10% will be used.
- 2. After approximately 1-week of wear, the Test lens will be superior to DT1MF with respect to clarity of intermediate vision.
- 3. After approximately 1-week of wear, the Test lens will be superior to DT1MF with respect to clarity of near vision.

All primary and secondary hypotheses must be met in order to test any exploratory hypotheses.

Exploratory Hypotheses

1. After 1-week of wear in the optimized lenses, the Test lens will be superior to DT1MF with respect to each of the following:

Group 1:

1. Overall Opinion

Group 2:

- 1. Blurred vision at close distances
- 2. Ease of re-focusing when you look from far to near
- 3. Clarity of vision when reading your cell phone

Group 3:

- 1. Consistent vision across all distance
- 2. Uninterrupted vision between and at all distances
- 3. Clarity of vision during daily activities

Group 4:

- 1. I experienced crisp clear vision at all distances
- 2. I experienced crisp clear vision in all lighting conditions

Group 5:

1. Clarity of vision when reading your computer screen

If exploratory hypotheses are tested, historical data will be combined with the current study data for the statistical analysis. See section 14 for more information.

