14.2. Sample Size Justification

This study was designed and powered to test for superiority of the Test lens relative to the DT1MF lens after 1-week of optimized lens wear with respect to clarity of vision in dim or low lighting and clarity of vision when reading in dim light. Additionally, this study was also powered to test the following after 1-week of optimized lens wear: superiority of the Test lens compared to DT1MF with respect to clarity of intermediate and near vision as well as non-inferiority with respect to clarity of distance vision.

The sample size for co-primary endpoints was estimated to achieve a minimum statistical power of 90% using a 2-sided type I error rate of 5% each and a minimum statistical power of 90% for the secondary endpoints using a 2-sided type I error rate of 1.67% each (5% familywise error rate).

Historical data from two study was utilized in the sample size calculation for this study. Both clinical studies, were 2x3 crossover designs with 1-week follow-up evaluation for the optimized lens wear. Table 6 below summaries the historical studies and Table 7 displays the estimated odds ratio and corresponding 95% CIs.

Table 6: Summary of Historical Studies Included in Sample Size Calculations

Study Number	Population	Design	Number Enrolled	Number Completed	Number included in PP population	Number in ITT population
Tuilibei		- 0				population
	Hyperopes	2x3	78	75	64	75
	Myopes	2x3	81	78	66	78

PP: Per-Protocol; ITT: Intent-to-treat

Table 7: Historical Odds Ratio Estimates and 95% CIs – Intent-to-Treat Population

		Estimated Odds	95% Confidence
Endpoint Type	Item	Ratio	Interval
Primary	Clarity of vision in low	1.67	(1.10, 2.53)
	lighting conditions		
	Clarity of vision when	1.88	(1.26, 2.82)
	reading in low light		
Secondary	Clarity of distance vision	1.27	(0.82, 1.98)
	Clarity of intermediate	1.98	(1.25, 3.13)
	vision		
	Clarity of near vision	2.28	(1.49, 3.48)

Odds ratios were calculated as Test over DT1MF

Odds ratio represents odds of having a more positive experience while wearing the Test lens compared to DT1MF

Primary and Secondary Sample Size Estimates

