14.6. Secondary Analysis

Clarity of intermediate and near vision will be analyzed using the intent-to-treat population while clarity of distance vision will be analyzed using the per-protocol population.

Clarity of Distance Vision

Subjective responses to this item (defined as *aval*) will be categorized in the same manner as described for the primary endpoints. The outcome will be analyzed and using the model described for Primary Analysis Plan B above.

Hypothesis Testing

Non-inferiority of the Test compared to DT1MF will be conducted as follows:

Ho: $OR \le 0.67$ Ha: OR > 0.67

Where, the OR represents the odds of having a more positive experience (Excellent or Very Good) while wearing Test compared to DT1MF. Non-inferiority of Test relative to DT1MF will be concluded if the lower limit of the simultaneous 95% CI (98.33% individually) is above 0.67. A cumulative odds ratio margin of 0.67 was utilized as this corresponds to nomore than a 10% difference using a reference rate of 0.58 for DT1MF.

Clarity of Intermediate and Near Vision

Subjective responses to these two items (defined as *aval*) will be categorized in the same manner as described for the primary endpoints. Association between these two endpoints will be assessed using the same test as the primary endpoints and will following the same strategy.

Hypothesis Testing

Regardless of which Plan (Primary Analysis Plan A or B) is implemented, superiority testing will be conducted separately for clarity of intermediate and near vision as follows:

Ho: $OR \le 1$ Ha: OR > 1

Where, the OR represents the odds of having a more positive experience (Excellent or Very Good) while wearing Test compared to DT1MF. Superiority of Test relative to DT1MF will be concluded if a lower limit of a simultaneous 95% CI (98.33% individually) is above 1.

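### The three secondary tests use plain Bonferroni; Holm in the favourable direction keeps the same familywise control and adds roughly 2.6 to 4.5 points of power for the all-three result the study needs

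*Combined protocol and SAP*

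**What the plan says.** Section 14.4 tests the secondary family only after both co-primaries have succeeded, each at two-sided 5%. For the family itself it specifies: "A Bonferroni correction will be utilized for the adjustment of multiple secondary hypotheses using a 2-sided type I familywise error rate of 5" per cent. Section 14.2 sizes the study accordingly, "for the secondary endpoints using a 2-sided type I error rate of 1.67% each", and Table 8 repeats 0.0167 in its alpha column.

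Section 14.6 turns this into one interval rule per endpoint. For distance: "Non-inferiority of Test relative to DT1MF will be concluded if the lower limit of the simultaneous 95% CI (98.33% individually) is above 0.67". For intermediate and near: "Superiority of Test relative to DT1MF will be concluded if a lower limit of a simultaneous 95% CI (98.33% individually) is above 1". The analysis sets differ: "clarity of distance vision will be analyzed using the per-protocol population", while the other two use the intent-to-treat population.

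Two passages make success on the whole family the target. Section 2.3: "All primary and secondary hypotheses must be met in order to satisfy the objective of this study". Section 14.4: "All primary and secondary hypotheses must be met in order to test any exploratory hypotheses". No step-down procedure is specified for the secondaries.

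**The concern.** Bonferroni holds every endpoint to 1.67% even after the other two have passed. That is stricter than 5% familywise control requires, and it costs most where only a clean sweep counts, as here. No error rate is at risk. What is lost is some probability of meeting the study's own objective and of reaching the exploratory tests.

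Some adjustment is still needed. Section 14.6 draws a separate conclusion for each secondary, and section 21 says the results are meant to support product claims, so a single endpoint may be claimed on its own. The question is only whether the same protection can be had at lower cost.

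**Working it through.** **Inputs.** Table 8, at alpha 0.0167: distance 99% (83 completers), intermediate 98% (110), near 96% (110). Co-primaries: 92% each. Table 6: 64 + 66 = 130 per-protocol subjects among 75 + 78 = 153 completers. The correlation between the three test statistics is not in the documents, so it is varied.

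**The plan's own figures.** 0.05/3 = 0.0167. Under independence the secondaries give 0.99 × 0.98 × 0.96 = 0.931 (stated: about 93%). The co-primaries give 0.92² = 0.846 (stated: about 85%). The product is 0.788. The stated 79.2% follows if the co-primary product is rounded first: 0.85 × 0.9314 = 0.792.

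**Noncentralities.** Only the lower confidence limit decides, so the one-sided steps are 0.025/3 = 0.00833, 0.025/2 = 0.0125 and 0.025, with critical z of 2.394, 2.241 and 1.960. Each Table 8 power gives a mean z of 2.394 + Φ⁻¹(power):
- distance: 2.394 + 2.326 = 4.720
- intermediate: 2.394 + 2.054 = 4.448
- near: 2.394 + 1.751 = 4.145

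Distance is analysed per protocol. At the Table 6 rate, 130/153 = 0.850, 110 completers yield about 93 (assumption: same rate here). Scaling by √(n/83) gives 4.997 at 93 (power 99.5%) and 5.434 at 110 (99.9%).

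**All-three power.** Bonferroni needs the smallest z to reach 2.394. Holm needs the largest to reach 2.394, the second 2.241 and the smallest 1.960. A hand check at independence with distance at 83: the powers at 1.960 are 0.9971, 0.9936 and 0.9855, with product 0.9764. Removing the few cases in which the two larger values miss their steps leaves 0.9762 exactly, a gain of 4.5 points. The other cases come from 10,000,000 simulated equicorrelated normal triples each.

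| Distance n | Correlation | Bonferroni | Holm | Gain (points) |
|---|---|---|---|---|
| 83 | 0 | 93.1% | 97.6% | 4.5 |
| 83 | 0.5 | 94.0% | 97.7% | 3.8 |
| 83 | 0.9 | 95.5% | 98.1% | 2.6 |
| 93 | 0 | 93.6% | 97.8% | 4.2 |
| 93 | 0.5 | 94.3% | 97.9% | 3.6 |
| 93 | 0.9 | 95.6% | 98.2% | 2.6 |
| 110 | 0 | 94.0% | 97.9% | 3.9 |
| 110 | 0.5 | 94.5% | 98.0% | 3.5 |
| 110 | 0.9 | 95.6% | 98.2% | 2.6 |

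A finer grid at 83 shows a minimum gain of about 2.3 points near correlation 0.97.

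**Overall power.** Multiplying by 0.8464, as the plan does, gives 78.8% to 82.6% (83, correlation 0) and 79.8% to 82.9% (93, correlation 0.5). The gain across the table is 2.2 to 3.8 points.

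**Familywise error, favourable direction, allowed 0.025** (correlation 0 / 0.5 / 0.9, 2,000,000 draws):
- three true nulls: 0.025 / 0.022 / 0.015 for both methods
- two true nulls, one very large effect: Holm 0.025 / 0.023 / 0.018, Bonferroni 0.017 / 0.016 / 0.012
- one true null, two very large effects: Holm 0.025 throughout, Bonferroni 0.008 throughout

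Holm uses the allowance that Bonferroni leaves unspent and stays within it, up to simulation error.

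**Agreement with the 98.33% interval.** The share of trials in which some endpoint is met under Holm while its 98.33% interval includes its null value is 4.2%, 3.7% and 2.8% at correlation 0, 0.5 and 0.9 (distance at 93).

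**The case against.** The strongest reply is that nothing is broken. Bonferroni is valid, sections 14.2, 14.4 and 14.6 agree on it, and its power is disclosed. It also has a function: every reported interval matches its decision. Holm gives that up, and the trials in which the two disagree are essentially the trials Holm gains. For a claims study that is a real trade-off, and it stands. It is why keeping Bonferroni remains defensible.

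Three points about the numbers also stand in part.

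- The 0.92 × 0.92 multiplier leaves the reading co-primary at its power for 69 completers. Scaled to 110, (1.960 + 1.405) × √(110/69) − 1.960 = 2.289, a power of 98.9%, and the multiplier becomes about 0.910. At 93 and correlation 0.5, overall power is then about 85.8% rising to 89.1%. The gain stays near 3 points, but the level near 79% should not be read as exact. Both multipliers also treat the secondaries as independent of the co-primaries.
- Table 8 is rounded to whole percentages. Rounding alone moves the gain at independence between about 3.6 and 5.3 points.
- Table 8 cannot be recovered by simply scaling Table 7. If the Table 7 intervals rest on the 153 intent-to-treat subjects (an assumption), scaling to 110 gives about 51%, 53% and 80% for distance, intermediate and near. Holm would then add about 8 to 19 points. The plan used a different method that cannot be rerun from the text, so this is a caveat on size and not on direction.

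One could also argue from the other side that a required clean sweep needs no adjustment at all. Unadjusted testing gives 97.6% at independence, almost the same as Holm, but it leaves single-endpoint conclusions unprotected.

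**Conclusion.** The point holds as an efficiency gain, not as an error. Directional Holm keeps the two-sided 5% familywise rate (2.5% in the tested direction) and rejects everything that Bonferroni rejects. It raises all-three power by about 2.6 to 4.5 points over correlations 0 to 0.9. Positive correlation is the more plausible case, because the same subjects answer all three items. At correlation 0.5 with 93 per-protocol subjects for distance, the gain is 3.6 points.

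The size rests on the Table 8 powers at face value, a common correlation, normal test statistics and the historical per-protocol rate. The direction rests on none of these.

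**What to change.** By protocol amendment before the mask is broken, replace Bonferroni with Holm for the three secondary hypotheses in sections 14.4 and 14.6:

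- Compute one-sided p-values for OR > 1 (intermediate, near) and OR > 0.67 (distance), and order them from smallest to largest.
- Compare them in turn with 0.00833, 0.0125 and 0.025, and stop at the first failure. Equivalently, the lower limits of the 98.33%, 97.5% and 95% two-sided intervals, in that order, must lie above each endpoint's own null value.
- State that an unfavourable result is never a rejection and never relaxes a later threshold.
- Report each interval at the level at which it was tested, next to the 98.33% interval labelled as conservative.
- Update the 1.67% wording, the Table 8 alpha column and the combined power in section 14.2, and carry the rule into the stand-alone SAP.

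The exploratory rule, "Within each grouping, a Bonferroni adjustment will be utilized to adjust for multiple testing", is outside this change and can stay as it is.

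The cost is wording, a recalculated power statement and submission of the revision to the IEC/IRB. Sample size and data collection do not change. If the sponsor prefers intervals and decisions that always agree, keep Bonferroni and give that reason in section 14.4.

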14.5. Primary Analysis

The primary analyses will be conducted on the intent-to-treat population.

Clarity of Vision in Dim or Low Lighting and Clarity of Vision when Reading in Dim light Subjective responses for co-primary endpoint will be the outcome (*aval*) defined as category one if a subject responds' 'Excellent' or 'Very Good', the outcome is defined as category two

if a subject responds' 'Good' and the outcome is defined as category three if a subject responds' 'Fair' or 'Poor'.

Since both co-primary endpoints assess various aspects of vision in dim or low light, the association between the two endpoints will be assessed using a Cochran-Mantel-Haenszel chi-square test using the Frequency PROCEDURE in SAS 9.4. If the association between the co-primary endpoints is statistically significant at an alpha=0.05 then the following analysis methods will be implemented:

Primary Analysis Plan A (If associate between co-primary endpoints is significant)

The outcomes for co-primary endpoints will be analyzed together using a hierarchical generalized linear mixed model (GLMM) with a multinomial distribution and the cumulative logit as the link function. Sequence of lens wear, period, lens type, first order carryover effect, item and the interaction between lens by item will be included as fixed effects. Site and subject nested within site will be included as random effects. Residual errors between measurements within the same subject and period across items will be modeled using an unstructured covariance (UN) structure. If this structure fails to converge then a variance component (VC) structure will be used. The Kenward and Roger method will be used for the calculation of the denominator degrees of freedom.¹⁶

Comparisons between the Test and DT1MF will be carried separately for each item out using 2-sided 95% confidence intervals (CIs) constructed for the odds ratio (Test over DT1MF). Superiority will be concluded if a lower limit of a 95% CI is above 1.

The Model:

Let $aval_{ijkl} = (aval1_{ijklm}, aval2_{ijklm}, aval3_{ijklm})$ denote the rating for l^{th} subject at the m^{th} site assigned to the k^{th} sequence for the i^{th} study lens during the j^{th} study period (i=1, 2; j=1, 2, 3; k=1,2; l=1.... n_m ; m=1,...,10). As previously described possible values of $aval_{ijklm}$ are $aval_{ijklm}$ =1 if a subject responds: 'Excellent' or 'Very Good', $aval_{ijklm}$ =2 if a subject responds: 'Good' and $aval_{ijklm}$ =3 if a subject responds: 'Fair' or 'Poor'. The Likelihood will be constructed as follows:

$$\begin{aligned} aval_{ijklm} \sim & \text{Multinomial } (p1_{ijklm}, p2_{ijklm}, p3_{ijklm}) \\ & p1_{ijklm} = aval1_{ijklm} \\ & p2_{ijklm} = aval2_{ijklm} - aval1_{ijklm} \\ & p3_{ijklm} = 1 - \sum_{X=1,2} pX_{ijklm} \end{aligned}$$

$$\text{Logit} \left(avalX_{ijklm} \right) = \beta_o + \beta_1 * sequence_k + \beta_2 * period1_j + \beta_3 * period2_j + \beta_4 * \\ lens_{i[j,k]} + \beta_5 * carry_{i[j,k]} + \beta_6 * item_h + \beta_7 * item_h * lens_{i[j,k]} + \delta_m + \gamma_{lm} + \varepsilon_{hijklm}$$

Where, β_0 is the intercept for X=1,2,3; $sequence_k=1$ if Test/DT1MF/DT1MF and $sequence_k=0$ if DT1MF/Test/Test; $period1_j=1$ if first period and $period1_j=0$ otherwise;

; $period2_j=1$ if second period and $period2_j=0$ otherwise; $lens_{i[j,k]}=1$ if Test and $lens_{i[j,k]}=0$ if DT1MF. $carry_{i[j,k]}=1$ if lens is Test and $carry_{i[j,k]}=0$ if lens is DT1MF.

Primary Analysis Plan B (If associate between co-primary endpoints is NOT significant)

The outcome will be analyzed separately for each primary endpoint using a generalized linear mixed model with a multinomial distribution and the cumulative logit as the link function. In each model, sequence of lens wear, period, lens type and first order carryover effect will be included as fixed effects. Site will be included as a random effect. Residual errors between measurements within the same subject across study periods will be modeled using an unstructured covariance (UN) structure. Comparisons between the Test and DT1MF will be carried out using 2-sided 95% confidence intervals (CIs) constructed for the odds ratio (Test over DT1MF). Superiority will be concluded if a lower limit of a 95% CI is above 1.

The Model:

Let $aval_{ijkl} = (aval1_{ijklm}, aval2_{ijklm}, aval3_{ijklm})$ denote the rating for l^{th} subject at the m^{th} site assigned to the k^{th} sequence for the i^{th} study lens during the j^{th} study period (i=1, 2; j=1, 2, 3; k=1,2; l=1.... n_m ; m=1,...,10). As previously described possible values of $aval_{ijklm}$ are $aval_{ijklm}=1$ if a subject responds: 'Excellent' or 'Very Good', $aval_{ijklm}=2$ if a subject responds: 'Good' and $aval_{ijklm}=3$ if a subject responds: 'Fair' or 'Poor'. The Likelihood will be constructed as follows:

$$aval_{ijklm} \sim \text{Multinomial } (p1_{ijklm}, p2_{ijklm}, p3_{ijklm})$$

$$p1_{ijklm} = aval1_{ijklm}$$

$$p2_{ijklm} = aval2_{ijklm} - aval1_{ijklm}$$

$$p3_{ijklm} = 1 - \sum_{X=1,2} pX_{ijklm}$$

$$\text{Logit } (avalX_{ijklm}) = \beta_o + \beta_1 * sequence_k + \beta_2 * period1_j + \beta_3 * period2_j + \beta_4 * lens_{i[j,k]} + \beta_5 * carry_{i[j,k]} + \delta_m + \varepsilon_{ijklm}$$

Where, β_o is the intercept for X=1,2,3; $sequence_k=1$ if Test/DT1MF/DT1MF and $sequence_k=0$ if DT1MF/Test/Test; $period1_j=1$ if first period and $period1_j=0$ otherwise; $period2_j=1$ if second period and $period2_j=0$ otherwise; $lens_{i[j,k]}=1$ if Test and $lens_{i[j,k]}=0$ if DT1MF. $carry_{i[j,k]}=1$ if lens is Test and $carry_{i[j,k]}=0$ if lens is DT1MF.

Hypothesis Testing

Regardless of which Plan (Primary Analysis Plan A or B) is implemented, superiority testing will be conducted separately for each co-primary endpoint as follows:

Ho: $OR \le 1$ Ha: OR > 1

CR-6479, v 3.0

Where, the OR represents the odds of having a more positive experience (Excellent or Very Good) while wearing Test compared to DT1MF. Superiority of Test relative to DT1MF will be concluded if a lower limit of a 95% CI is above 1.

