5. TEST ARTICLE ALLOCATION AND MASKING

5.1. Test Article Allocation

The study lenses will be worn in a bilateral and random fashion using a 2x3 crossover design. A computer-generated randomization scheme will be used to randomly assign subjects, in blocks of 2, to one of the two lens wear sequences: Test/DT1MF/DT1MF or DT1MF/Test/Test. The randomization scheme will be stratified by site. The random scheme will be generated using the PROC PLAN procedure from Statistical Analysis System (SAS) Software Version 9.4 or higher (SAS Institute, Cary, NC).¹⁵

The study site must follow the randomization scheme provided and complete enrollment per the randomization list and not pre-select or assign subjects. Randomization will be performed at visit first visit prior to the first fitting. The following must have occurred prior to randomization:

- Informed consent must have been obtained.
- The subject must have met all eligibility criteria.
- The subject's screening and baseline information must have been collected.

When dispensing test articles, the following steps should be followed to maintain randomization codes:

- 1. Investigator or designee (documented on the Delegation Log) will consult the lens fitting schedule to obtain the test article assignment for that subject prior to dispensing.
- 2. Investigator or designee will record the subject's number on the appropriate line of the lens fitting schedule.
- 3. Investigator or designee will pull the appropriate test articles from the study supply. All test articles that are opened, whether dispensed (placed/fit on eye or dispensed outside the clinical site) or not, must be recorded on the Test Article Accountability Log in the "Dispensed" section.

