Sample size estimates for each co-primary and secondary endpoint were carried out separately using an approximation of the power of an F-test derived from the non-centrality parameter calculated from the observed F statistic of a linear model. Each endpoint was analyzed individually using a generalized linear mixed model with a multinomial distribution and the cumulative logit as the link function. Sequence of lens wear, period, lens and first order carryover effect were included in the model as fixed effects. Study nested within site was included as a random effect (G-side). Errors between measurements within the same subject across periods was model using a variance component (VC) covariance structure. The Kenward and Roger method was used for the calculation of the denominator degrees of freedom.¹⁶

To estimate the sample size for each co-primary and secondary endpoints, the odds ratio and the cumulative log-odds from the model described above for each endpoint was used to create a new dataset with the same structure and design as the historical studies. This new dataset was then analyzed using a generalized linear model with a multinomial distribution and the cumulative logit as the link function. Lens type was included as the only fixed effect; errors between measurements within the same subject across periods was model using a variance component (VC) covariance structure. The Kenward and Roger method was used for the calculation of the denominator degrees of freedom. The statistical power of each endpoint was calculated using the F-statistics as Power=P(F[Fcrit, v, ncp] > Fcrit); where Fcrit is the critical value of the central F distribution (Fcrit= $F_{[numdf,dmdf,0,alpha]}$) under Ho (Ho: centrality param = 0), v is the magnitude of the departure from Ho and ncp is the non-centrality parameter (Stroup).¹⁷

Table 8 displays the sample size estimates and associated power by endpoint. As indicated below, co-primary endpoints were powered \sim 92% individually yielding a combined power of \sim 85%. With respect to secondary endpoints, each hypothesis was also powered to at least \sim 96% power provided a combine power of \sim 93%. Therefore, the overall combined study power for co-primary and secondary hypotheses is 79.2% and is considered reasonable to support any conclusions from these analyses.

Table 8: Sample Size Estimates by Endpoint

Endpoint			# of Subjects	
Type	Item	Alpha	Complete	Power (%)

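### The carryover term in both primary models is coded identically to the lens term, so the carryover-adjusted Test versus DT1MF odds ratio cannot be estimated as written

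*Combined protocol and SAP*

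**What the plan says.** Section 5.1 randomizes subjects to "one of the two lens wear sequences: Test/DT1MF/DT1MF or DT1MF/Test/Test", over three periods.

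Section 14.5 specifies two cumulative-logit models. For Plan A (co-primary items analysed jointly): "Sequence of lens wear, period, lens type, first order carryover effect, item and the interaction between lens by item will be included as fixed effects". Plan B (each item separately) has sequence, period, lens type and first-order carryover. The model fitted to the historical data in Section 14.2 was described in the same way: "Sequence of lens wear, period, lens and first order carryover effect were included in the model as fixed effects".

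The notation under each model defines the lens term as "lens_{i[j,k]}=1$ if Test and $lens_{i[j,k]}=0$ if DT1MF" and the carryover term as "carry_{i[j,k]}=1$ if lens is Test and $carry_{i[j,k]}=0$ if lens is DT1MF". The wording is the same in both plans. Neither definition mentions an earlier period or gives a value for Period 1.

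The plans handle within-subject correlation differently. Plan A has a random effect for subject within site. Plan B has none, and instead: "Residual errors between measurements within the same subject across study periods will be modeled using an unstructured covariance (UN) structure".

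Section 14.6 sends distance vision straight to Plan B: "The outcome will be analyzed and using the model described for Primary Analysis Plan B above". Intermediate and near vision follow the same choice between A and B as the co-primary items.

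**The concern.** A first-order carryover covariate should record the lens worn in the preceding period. As printed, it records the lens indexed by the current period and sequence, so it duplicates the lens covariate. It also gives subjects who start on Test a carryover in Period 1, before which no study lens was worn.

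Programmed literally, the software will either report the lens contrast as non-estimable or remove one of the two columns. In the first case someone has to decide, after the plan was fixed, what the model was meant to be. In the second, the fit becomes a model without carryover and the stated adjustment is not done. The definition sits in the model behind both co-primary superiority tests and all three secondary tests.

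**Working it through.** The plan gives no figure to reproduce here. The check is on the structure of the fixed-effect matrix, and then on what follows if carryover is dropped.

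**1. Columns as printed** (sequences from Section 5.1, coding from Section 14.5; values for Periods 1, 2, 3)

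| Sequence | lens | carry as printed | carry from preceding lens |
|---|---|---|---|
| Test/DT1MF/DT1MF | 1, 0, 0 | 1, 0, 0 | 0, 1, 0 |
| DT1MF/Test/Test | 0, 1, 1 | 0, 1, 1 | 0, 0, 1 |

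**2. Rank.** Plan B's columns are intercept, sequence, two period indicators, lens and carry. Plan A adds item and item-by-lens.

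| Model | Columns | Rank as printed | Rank with preceding-lens coding |
|---|---|---|---|
| Plan B | 6 | 5 | 6 |
| Plan A | 8 | 7 | 8 |

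As printed, the lens coefficient β4 alone is not estimable in either plan, and neither is the carry coefficient β5. The sum β4 + β5 is estimable in both, as is β4 + β5 + β7 (the second item's contrast) in Plan A. With preceding-lens coding the lens effect is estimable in both plans, for each item in Plan A.

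**3. Shift in the lens estimate if carry is dropped.** This is a linear approximation with generalized least squares, equal variances, complete data and equal sequence sizes. Write r12, r13 and r23 for the within-subject correlations between periods. Regressing the correctly coded carry column on the remaining columns gives

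shift per unit of carryover = −(r12 − r13) / [2(1 − r23)].

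The documents give no correlations, so those below are assumed. Variances are for one subject per sequence with unit variance.

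| r12 / r13 / r23 | Shift | Lens variance without carry | Lens variance with carry |
|---|---|---|---|
| 0 / 0 / 0 | 0 | 0.750 | 0.750 |
| 0.3 / 0.3 / 0.7 | 0 | 0.625 | 0.625 |
| 0.5 / 0.45 / 0.55 | −0.056 | 0.411 | 0.412 |
| 0.4 / 0.3 / 0.6 | −0.125 | 0.544 | 0.550 |
| 0.3 / 0.2 / 0.7 | −0.167 | 0.667 | 0.675 |
| 0.5 / 0.25 / 0.5 | −0.25 | 0.469 | 0.500 |
| 0.2 / 0.3 / 0.7 | +0.167 | 0.667 | 0.675 |

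The 0.3/0.2/0.7 row, worked: −(0.3 − 0.2) / [2 × (1 − 0.7)] = −0.1/0.6 = −0.167.

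The shift is zero whenever r12 = r13. Plan A's subject random effect implies equal correlation across periods, so its shift is zero. With an assumed subject correlation of 0.4 and a within-period item correlation of 0.5, Plan A's lens variance is 0.4375 with and without carry.

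**4. On the odds-ratio scale.** Take the historical odds ratios in Table 7 as true values, and assume a carryover log odds ratio of 0.2 to 0.5:

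- Dim-light clarity, shift −0.167: 1.67 × exp(−0.167 × 0.2) = 1.62, and 1.67 × exp(−0.167 × 0.5) = 1.54.
- Distance, shift −0.167: 1.27 becomes 1.23 to 1.17.
- Dim-light clarity, shift +0.167: 1.67 becomes 1.73 to 1.82.
- Dim-light clarity, shift −0.056: 1.67 becomes 1.65 to 1.62.

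**The case against.** The strongest reply is that this is a slip of notation. The definition says only that the lens is Test, and current lens is inferred from the shared subscript. First-order carryover ordinarily means the preceding period, so a competent programmer would probably code the lag. Section 14.2 reports that the term was included in the historical models, and Table 7 shows finite odds ratios, which is consistent with a workable coding already in use. Section 14.1 calls Section 14 a general description and leaves detail to a stand-alone SAP that was not available for this review. A non-estimable contrast would also tend to show itself before any result was produced.

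Much of this is fair on intent and consequence. The overall Test versus DT1MF contrast can still be obtained, the sizes above rest on assumed values, and Plan A is unaffected by a dropped column. It does not rescue the definition, which is complete and printed twice without a lag or a Period 1 value. The historical fits are weak evidence, because a silently dropped column would also give finite odds ratios. Section 14.10 says the analysis will follow these sections and that any change must be documented and justified, so even the obvious repair would have to be reported as a change.

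**Conclusion.** The concern holds: the models as written are rank-deficient and cannot separate lens from carryover. This is an error of definition. The two-sequence, three-period design supports the intended term at full rank.

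The practical effect is probably small. It is zero under Plan A. Under Plan B it needs both real carryover and unequal period 1–2 and 1–3 correlations, and an unstructured covariance does not guarantee that they are equal. Plan B always applies to the distance non-inferiority test. It applies to the other four tests only if the relevant association test is not significant. Carryover is also limited by the 8 to 12 days of wear between a lens switch and the endpoint (3±1 plus 7±1 days). The shifted odds ratios are illustrations under the linear approximation and the assumed correlations and carryover, not predictions.

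This should be fixed before database lock because the same definition underlies every confirmatory odds ratio.

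**What to change.** In both model definitions in Section 14.5, and in the SAP, index carryover to period j−1 within sequence k: 1 if the lens worn in the preceding period was Test, 0 if it was DT1MF, and 0 for every subject in Period 1. State that the odds ratio tested is the lens contrast with carryover held fixed.

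The cost is one sentence in each of two definitions and the matching line of the programming specification. Data collection does not change. The stated sample size is unaffected, since the power model in Section 14.2 had lens as its only fixed effect. Fitting the term correctly costs no precision under equal correlation. Under the unequal correlations tried, the lens variance rises by about 1% (0.667 to 0.675) at 0.3/0.2/0.7 and by about 7% (0.469 to 0.500) at 0.5/0.25/0.5.
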